The primary objective was a reduction of ≥ 2 of the rumination score measured by question 32 of the Rome IV diagnostic questionnaire for adult functional disorders (Rome IV) at baseline and at the 6-month control. Secondary objectives were improvement of HRQoL and functional capacity scores, reduction of anxiety and depression scores, and disappearance of intragastric pressure peaks in esophageal manometry at the 6-month control.

Patients

We recruited rumination patients from gastroenterology outpatient clinics to our study at the Helsinki University Hospital during the study period of Jan. 1, 2022, to Dec. 31, 2023.

The inclusion criteria for the study included age between 15-70 years, Finnish as the native language, fulfillment of the clinical Rome IV rumination criteria, a rumination score of ≥ 6 in the Rome IV diagnostic questionnaire for adult functional disorders (rumination occurring most days a week),

previous gastroscopy, esophageal manometry and MII-pH. We aimed to recruit patients, who had previously had esophageal manometry performed with intragastric pressure increases ≥ 30 mmHg immediately preceding the rumination experienced by the patient, suggestive of rumination. Patients with only a clinical diagnosis of rumination syndrome were also accepted in the study, because previous to our study, Nutridrink instead of a solid meal was used when performing standard esophageal manometry in our institution and thus might not always detect rumination.

The exclusion criteria comprised large hiatal hernia, severe esophagitis, previous fundoplication, eating disorder, BMI under 14, pregnancy, significant cognitive disorder, and any other condition hindering outpatient visits.

Study protocol

At the baseline visit, cases were checked to ascertain whether they fulfilled the inclusion or exclusion criteria. Previous conditions, investigations, use of medications, and symptoms were registered. All patients obtained written information about the study, about the behavioral and functional nature of rumination, and its therapy including diaphragmatic breathing exercises and thoracic and abdominal muscle relaxations. Written consent was obtained from all patients.

From the baseline visit the patients were referred to the speech therapist for five one-hour sessions, and to the physiotherapist for two one-hour sessions and to the psychologist's and the dietitian's consultation.

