Symptoms, HRQoL, depression, anxiety, and functional capacity were evaluated by questionnaires given to the patients and weight were defined at onset of the study and at the 6-month control. Esophageal manometry with a pancake meal (191 kcal) was performed at the 6-month control. The study protocol is displayed in the figure below (Figure 1).

Questionnaires

Symptom severity was evaluated by the Rome IV questionnaire for adult functional disorders (12). The question 32 of the Rome IV diagnostic questionnaire for adult functional disorders scores the rumination frequency as follows: "In the last 3 months, how often did food come back up into your mouth after you swallowed it ?, 0 = never, 1= fewer than 1 day a month, 2 = 1 day a month, 3 = 2-3 days a month, 4 = 1 day a week, 5 = 2-3 days a week, 6 = most days, 7 = every day, 8 = multiple times per day or all the time".

Depression was evaluated by the Beck Depression Inventory (BDI), anxiety by the Beck Anxiety Inventory (BAI), HRQoL by the 15D, a 15-dimensional measure of health-related quality of life and functional capacity by the World Health Organization disability assessment schedule 2.0 (WHODAS 2.0) (13-16). The patients filled out the questionnaires at home and mailed them to the hospital.

Behavioral therapy

The therapy comprised psychoeducation about the nature of rumination as a behavioral disorder and means of dealing with the symptom including diaphragmatic breathing exercises and guided eating performed by the speech therapist, and mind-body oriented physiotherapy, all aiming at habit reversal.

The patients were first taught the mechanisms of rumination at the speech-therapist visits. We considered it essential for the study's success for the patients to understand the functional nature of rumination. The next step was to teach them diaphragmatic breathing and to relax abdominal muscles. Finally, the patients were trained to apply these exercises during meals and to continue them at home.

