The patients were referred to a dietitian trained in functional behavioral disorders for psychoeducation, to evaluate food and meal and related mental threats, and to ensure a sufficient diet. The primary goal of the dietitian's psychoeducation was to ensure that patients did not have negative expectations regarding food or nutrients. It is common in functional diseases that patients develop learned experiences and expectations that become self-predictive. The dietitian interviewed the patients to discover which food products the patients avoided due to them provoking rumination or other gastrointestinal symptoms such as diarrhea, to learn if rumination played a role in managing anxiety, and to discern if the patients had lost weight prior to or during the study. No special diet instructions or foods were recommended to be avoided due to rumination. The dietary goal was to normalize eating.

Statistical analysis

SPSS software was used to perform the statistical analysis. The question 32 of the Rome IV diagnostic questionnaire for adult functional disorders was used for the sample size calculation. The hypothesis was that the mean (\pm standard deviation) self-perceived frequency of rumination at baseline would be 6 ± 2 (most days a week) because this was the inclusion criteria for the study and the symptom improvement after therapy would be ≥ 2 resulting in the score of 4 ± 2 (once a week) at the 6-month control. Using the Sample Size Calculator of ClinCalc.com the number of patients required was 8 to obtain 80% power and significance of $P < 0.05$. The non-parametric Wilcoxon's signed rank test and Mann-Whitney test for the analysis of related samples were used for the

comparison of differences in the distributions of variables between the baseline and the 6-month control except for the 15 dimensions of HRQoL which were analyzed by the paired samples t-test. The independent samples t-test was used to compare the mean 15D results of the patients at baseline with those of age-standardized general Finnish population. Apart from the manometry and 15D results which are displayed as means and standard deviations, all other results are displayed as medians and interquartile ranges.

Figure 1.

References

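### Mann-Whitney, an independent-groups test, is named beside Wilcoxon signed-rank for the paired baseline versus 6-month comparisons, including question 32

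*Combined protocol and SAP*

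**What the plan says.** The Statistical analysis section assigns two rank tests to one purpose. It names them as follows: "The non-parametric Wilcoxon's signed rank test and Mann-Whitney test for the analysis of related samples were used for the". The purpose, given in the rest of that sentence, is a "comparison of differences in the distributions of variables between the baseline and the 6-month control". The only exception is the 15 dimensions of the 15D, which go to a paired t-test. Question 32 is not a 15D dimension and no other test is named for it, so this sentence governs it. The sentence also covers BDI, BAI and WHODAS 2.0, and weight, since the Study protocol section says that questionnaires and "weight were defined at onset of the study and at the 6-month control".

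One comparison between independent groups is described, patients against the general population on 15D, and it has its own test: "The independent samples t-test was used to compare the mean 15D results of the patients at baseline".

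The Objective section sets the target as a change in points: "The primary objective was a reduction of ≥ 2 of the rumination score measured by question 32". It attaches no P value to that target. On sample size, the plan says "the number of patients required was 8 to obtain 80% power and significance of" P < 0.05.

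**The concern.** Each patient supplies a baseline and a 6-month value. Signed-rank works on the within-patient differences. Mann-Whitney treats the two sets of values as coming from different people. Calling it a test for related samples is therefore an error of method, not a matter of preference.

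As written, a reader cannot be certain which of the two tests lies behind a given P value. Any paired P value that came from Mann-Whitney would be wrongly derived. With about 8 patients, the two tests can fall on opposite sides of 0.05 on the same data.

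**Working it through.** **1. Does the plan's own figure point to a paired analysis?** Inputs from Statistical analysis: baseline 6 ± 2, follow-up 4 ± 2, so a change of 2; 80% power; P < 0.05, taken as two-sided because sidedness is not stated.

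- One-sample or paired formula with SD 2: n = ((1.960 + 0.842) × 2/2)² = 7.85, rounded up to 8. This reproduces the stated 8.
- Independent groups: 2 × 7.85 = 15.70, so 16 per group. This does not.

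The stated number fits a one-sample or paired reading. It is not put in doubt by this point.

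**2. Can the two tests reverse each other?** Two invented data sets, admissible for question 32 (entry rule "a rumination score of ≥ 6 in the Rome IV diagnostic questionnaire for adult functional disorders"; top of scale "8 = multiple times per day or all the time"), n = 8:

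- (i) 6,6,6,7,7,7,8,8 to 6,5,5,6,6,6,7,7. One zero difference is dropped and the other seven are all drops of 1, so exact signed-rank P = 2/2⁷ = 0.016. For Mann-Whitney, U = 49 against an expected 32, tie-corrected SD 8.96, z = 17/8.96 = 1.90, P = 0.058 (exact 0.090).
- (ii) 6,6,6,6,6,7,8,8 to 8,5,5,5,5,4,4,4. Signed-rank sums are 31 and 5 against an expected 18, tie-corrected SD 7.04, z = 13/7.04 = 1.85, P = 0.065 (exact 0.094). For Mann-Whitney, U = 57, SD 9.25, z = 25/9.25 = 2.70, P = 0.007 (exact 0.008).

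So reversals are possible in either direction. These sets are not typical: their baseline to follow-up correlations are 0.91 and -0.60, outside the range used in step 3. In (i) the mean drop is 7/8 = 0.875 and nobody drops by 2.

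**3. How often would they disagree?** The documents give no correlation, SD of change or enrolled number, so these are assumptions. Baseline is uniform on 6, 7, 8. Follow-up = intercept + b × baseline + normal residual, rounded and clipped to 0-8, with the intercept set to give a mean drop of 2. Residual SD 2 follows the plan's 4 ± 2. Slopes b of 0, 0.5 and 1 then give correlations 0.00, 0.20 and 0.37. With 40,000 trials per cell and n = 8:

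| | b = 0 | b = 0.5 | b = 1 |
|---|---|---|---|
| Exact: Mann-Whitney power | 62.9% | 62.1% | 58.4% |
| Exact: signed-rank power | 51.3% | 56.8% | 60.4% |
| Exact: opposite verdicts | 15.4% | 13.4% | 13.3% |
| Asymptotic: Mann-Whitney power | 65.6% | 64.8% | 61.3% |
| Asymptotic: signed-rank power | 63.1% | 70.0% | 74.0% |
| Asymptotic: opposite verdicts | 11.7% | 12.9% | 16.6% |

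Allowing for repeat runs, disagreement is about 11-17%. Neither test is uniformly the more powerful.

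Sensitivity of the disagreement (asymptotic):

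- Residual SD 1 instead of 2, same slopes, n = 8: about 1-5%.
- Larger samples, SD 2: 7-12% at n = 12, 4-6% at n = 16, about 1% at n = 24.

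**4. No true change.** With both visits uniform on 6-8, the chance that at least one of the two tests is significant was 3.1-6.0% with asymptotic P values (correlation 0 to 0.3, n = 8 to 24). With exact P values at n = 8 it was 3.1% at correlation 0 and 1.0% at 0.3. These are results for the settings simulated, not a ceiling: runs with negative correlation gave about 10-17%.

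**The case against.** The strongest reply is that the paired intention is plain. Signed-rank is named first, the sentence speaks of related samples, the parallel 15D comparison has a paired t-test, and the stated 8 fits a paired or one-sample formula. On that view Mann-Whitney is a stray word. This largely stands, and it is why a drafting slip is the likeliest explanation. It does not make the sentence correct.

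A second reply is that Mann-Whitney may have been meant for a subgroup contrast, for example patients with manometric evidence of rumination against those with a clinical diagnosis only, both of whom the Patients section admits. That is possible, but the plan describes no such comparison, and the sentence ties the test to baseline versus 6 months.

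A third reply is that the disagreement figure depends on assumptions. That stands in full: halving the residual SD or enrolling 24 patients nearly removes it.

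A reader might also infer much larger effects. An unbounded normal model with SD 2 at both visits gives 26% disagreement at correlation 0.5 and 45% at 0.75. Those figures do not carry over to question 32. With entry limited to 6-8, no score lies more than 1 from the midpoint 7, so the baseline SD cannot exceed about 1.

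**Conclusion.** The sentence is wrong as written: it gives an independent-groups test to paired data, and the plan describes no other use for that test. Confidence in that is high. The practical effect is modest and conditional. Disagreement is about 11-17% at n = 8 under the bounded model with residual SD 2, about 1-5% with residual SD 1, and about 1% at n = 24 with SD 2.

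The documents do not support three stronger readings:

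- That the primary result rests on the wrong test. Nothing shows that any paired result was computed with Mann-Whitney, and the primary objective is a reduction of at least 2 points without a P value criterion.
- That the slip pushes results in one direction. Either test can be the more favourable.
- That the false-positive risk is capped at about 6%. That holds only for the settings simulated with correlation 0 to 0.3, and the risk is higher if the correlation is negative.

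Severity: minor.

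**What to change.** Name the two-sided Wilcoxon signed-rank test as the single test for the question 32 change and for the other paired non-15D variables (BDI, BAI, WHODAS 2.0, weight). Delete Mann-Whitney from the baseline versus 6-month comparisons, or state the independent-group comparison that it serves.

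The document is dated 2024-9-10, after the study period ended on 31 December 2023, and is written in the past tense. The correction should therefore say which test was actually run, and any paired result obtained with Mann-Whitney should be rerun with signed-rank. It would help to add how zero differences and ties were handled and whether P values are exact or asymptotic, but that is missing detail and not part of the error.

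Cost: one sentence, plus a small rerun only if Mann-Whitney was in fact used on paired data.
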